11. STUDY PROCEDURES

Verbal eligibility check

Prior to commencing the study, participants will be contacted via telephone and an initial verbal eligibility check will take place (approx. 30 min conversation). Following this, potentially eligible participants will be invited to visit the Sir Peter Mansfield Imaging Centre for study assessment visit one.

Within 72 hours of each visit to a research site (assessment visits and supervised training sessions), participants will be contacted via telephone by a member of the research team and a verbal COVID-19 symptom screening questionnaire will be administered. As per site guidelines, the questionnaire will be site-specific to Leicester and Nottingham sites. Furthermore, the COVID-19 symptom screening questionnaire will be further completed by participants upon arrival at each study site visit to further screen for symptoms.

Assessment visit 1 - Sir Peter Mansfield Imaging Centre (University of Nottingham)

Informed consent

Before any study related procedure can take place, the participant must sign and date the most recent approved version of the Informed Consent Form. Before consent is obtained the responsible individual will ensure that the participant fully understands all aspects of the study. It will also be clearly stated that the participant is free to withdraw from the study at any time, for any reason, without prejudice to future care, and with no obligation to give the reason for withdrawal. If a participant withdraws from the study but does not withdraw their consent, then data already obtained may be used for the study. If a participant has withdrawn due to an adverse event, a healthcare professional will follow up as appropriate.

The consent form will be signed and dated based up on an informed decision. The consent process will be performed by someone who has received consent training, has been authorised by the Chief Investigator, and is named on the delegation of authority log. The original signed form will be retained at the study site and copy will be given to the participant. A third copy will be posted to the participant's GP.

Questionnaires

Participants will complete several pen and paper based questionnaires to assess their eligibility to participate in the study and to provide baseline study data. These will include the following:

- Physical Activity Readiness Questionnaire - to determine participants' readiness to exercise and/or contraindications
- Loughborough University Health Screen Questionnaire – to obtain an overview of participants' medical history, current medications and family history of disease
- Sir Peter Mansfield Imaging Centre Magnetic Resonance Safety Screening Form – to assess potential contraindications to MRI

- Demographics & contact details – to determine participants' date of birth, ethnicity and postal address

Anthropometry, blood pressure and finger prick blood test

Height, body mass and waist circumference will be measured using standard techniques and body mass index (BMI) will be calculated. Body fat percentage will be estimated using bioelectrical impedance analysis. Blood pressure will be assessed using an automated monitor after participants have sat quietly for 10 minutes (average of three measurements). A finger prick blood test will be taken to check preliminary eligibility (HbA1c, glucose, lipids) using a point-of-care device.

Magnetic resonance imaging (MRI)

MRI data will be acquired using a 3T Philips Ingenia MRI scanner. Liver fat quality indices and total intrahepatocellular liver fat fractions will be determined using ¹H-MRS via the quantification of individual lipid group peaks. Liver inflammation, visceral adipose tissue and subcutaneous abdominal adipose tissue will be measured via MRI. The techniques used to measure these outcomes have been validated and published previously [13,18,19].

Familiarisation with weighed food records and physical activity monitors

Participants will be provided with a wrist worn (watch-like) physical activity monitor (GENEactiv) that they will wear 24 h/day for the next seven days. Participants will also be shown how to keep an accurate weighed food record and will be provided with food scales and diary to facilitate a three-day record within the next seven days (two week and one weekend day).

After this session, MRI scans will be assessed to examine whether or not participants have an amount of liver fat that is high enough for inclusion in the study (> 5.56%). If liver fat is less than this then participants will not be permitted to participate. If liver fat is equal to or greater than this level, then participants will be invited to attend study assessment visit two.

Assessment visit 2 - Leicester General Hospital (Leicester Diabetes Centre) or Queens Medical Centre Hospital (NIHR Nottingham BRC)

Fasting blood sample

Participants will be asked to attend the second study assessment visit having not eaten since the prior evening. These visits will therefore occur in the morning (before 10:30). At the start of this visit participants will provide a fasting venepuncture blood sample (50 mL blood) after having sat down for 10 minutes. This sample will be collected from an antecubital vein by an individual trained and experienced in phlebotomy. One blood bottle will be sent to hospital pathology labs for the analysis of glycated haemoglobin. The remaining samples will be processed immediately and stored until the end of the trial within -80°C freezers at the research sites. Following the last participants visit, samples will

be transported to Loughborough University (at -80°C) by a commercial courier. Samples will then be analysed in batch for:

- Lipids
- C-reactive protein
- Liver enzymes
- Glucose
- Insulin
- Nonesterified fatty acids
- Hepatokines
- Inflammatory proteins
- Genotype (gene variants linked to NAFLD)

Medical evaluation and aerobic fitness

A healthcare professional will take a full medical history from participants in order to identify any factors that may prohibit individuals from completing the study. Blood pressure will be measured, and a 12 lead ECG and a physical examination* will also be performed. Finally, a symptom limited progressive treadmill exercise test will be undertaken on a treadmill. This test will require participants to exercise at increasingly harder intensities until volitional exhaustion. A clinical professional will monitor participants' blood pressure and ECG during this test which will be terminated if clinically indicated.

* The physical examination is optional and dependent on findings from Medical History and 12 Lead ECG. It is to be performed by individuals qualified to do physical examinations.

Randomisation

After visit two, participants entering Part B of the study will be randomised (1:1) to condition (exercise training or control). Randomisation will be performed by the trial statistician ([name]) (see section 13 for additional details). The involvement of participants who are only completing Part A of the study will end at this point.

Six week intervention

Participants randomised to control will receive no interventions during the six-week intervention phase. During this time, control participants will be asked to not change any aspects of their lifestyles. Ahead of week five, participants will be posted a physical activity monitor to wear continuously during week five and six. Participants will also complete weighed food diaries during week five (two weekdays and one weekend day).

Participants randomised to exercise training will complete four exercise training sessions per week during the six-week intervention. Each week, at least one session will be supervised by the research team whilst the remaining sessions will consist of participants undertaking brisk walking on their own. All exercise sessions will be composed of continuous moderate-intensity exercise and last 35 - 50 minutes in duration (depending on intervention week). The specific details relating to these training sessions can be seen in section 12 (Table 2).

Assessment visit 3 (post-intervention) - Sir Peter Mansfield Imaging Centre (University of Nottingham)

The assessments undertaken at visit three will be a repeat of those completed during visit one.

Assessment visit 4 (post-intervention) - Leicester General Hospital (Leicester Diabetes Centre) or Queens Medical Centre Hospital (NIHR Nottingham BRC)

The assessments undertaken at visit four will be a repeat of those completed during visit two except that a medical examination will not be performed.

12. TREATMENT OF TRIAL PARTICIPANTS

Overview of procedures

This study will consist of two parts (A and B) and will include two discrete groups of participants.

1. Obese men with NAFLD – will complete Part A only
2. Obese men with NAFLD and T2DM/prediabetes – will complete Part A and B

Table 1 provides an overview of the procedures that participants will undertake as part of this study.

Table 1: summary of trial procedures for study participants

Visit	Duration	Procedure(s)
Study Part A – all participants		
Telephone interview	30 min	Verbal eligibility check against inclusion / exclusion criteria
Assessment visit 1 (SPMIC)	2 h	Informed consent, study questionnaires, anthropometry, blood pressure, finger prick test, MRI scan
Assessment visit 2 (QMC or LGH)	2 h	Fasting blood sample, medical examination, peak oxygen uptake test
Study Part B – obese men with NAFLD & T2DM/prediabetes only		
3-20 Exercise training (supervised sessions at QMC, LGH or Loughborough University)	1 h per session	Heart rate, RPE
Assessment visit 3 (SPMIC)	2 h	Study questionnaires, anthropometry, blood pressure, MRI
Assessment visit 4 (QMC or LGH)	2 h	Fasting blood sample, peak oxygen uptake test

RPE - ratings of perceived exertion, MRI magnetic resonance imaging, HbA1c – glycated haemoglobin, SPMIC – Sir Peter Mansfield Imaging Centre, QMC – Queens Medical Centre Hospital, LGH - Leicester General Hospital

At the beginning of the study, all potential participants will complete a telephone interview to verbally assess eligibility for the study (age, sex, activity status, smoking status, habitual alcohol intake,

understanding of English, medical history, medication use, contraindications to the study procedures, willingness and ability to undertake six weeks exercise training). Participants who are potentially eligible will then be invited to attend the Sir Peter Mansfield Imaging Centre located on the University of Nottingham campus for the first study assessment visit.

Prior to each visit to a study site (including assessment visits and supervised training sessions) participants will be contacted via telephone by a member of the research team within 72 hours of their visit to complete a site-specific COVID-19 symptom screening questionnaire. Upon arrival at the study site, participants will verbally complete the COVID-19 symptom screening questionnaire again with a member of the research team.

Before participants' first study visit, they will be asked to consume a normal diet i.e. no unusual feasting or energy restriction, in the prior 24 h. No alcohol or high caffeine containing foods will be permitted during this time. Participants will also be asked to attend the research centre in the morning having not eaten since the prior evening (after 22:00). At this initial visit, a member of the research team will check participants' understanding of the study and written informed consent will be obtained. Participants will then complete additional screening and eligibility assessments as detailed in section

11. Before leaving the research centre, participants will have a physical activity monitor attached to them (watch like device) that they will wear for the next seven days. They will also be provided with food weighing scales and a food diary to assist them in providing a three-day weighed food record (two week and one weekend day) within the subsequent seven days.

After study assessment visit one, the research team will contact participants by telephone to inform them whether or not they have sufficiently high liver fat to permit their inclusion in the study. If so, study assessment visit two will be arranged. If participants do not meet the inclusion criteria, they will be asked to post back the food diary and physical activity monitor using a prepaid envelope already provided. These individuals will take no further part in the study.

Participants' second assessment visit will take place at the Queens Medical Centre Hospital (Nottingham) or the Leicester General Hospital (depending on preference). Ahead of this visit, they will be asked to consume a 'normal diet' in the 24 h beforehand. No alcohol or high caffeine containing foods will be permitted during this time. Participants will also be asked to attend the research centre in the morning having not eaten since the prior evening (after 22:00). Participants will bring their physical activity monitor and food diary with them to this visit. During this visit participants will undertake all of the assessments outlined in section 11. The completion of this visit will mark the end of procedures for participants who are only completing Part A of the study (obese men with NAFLD). In due course, a

member of the study team will contact these individuals via telephone in order to discuss the provision of feedback in relation to their results.

Participants progressing to Part B of the study (obese men with NAFLD and T2DM/prediabetes) will then be randomised to exercise training or control for six weeks. Participants will be made aware of their group assignment via telephone. Control participants will undergo no interventions and will be asked not to alter any aspect of their lifestyle during the next six weeks. Ahead of week five, control participants will receive a physical activity monitor and food diary in the post to enable them to record their habitual physical activity and food intake during weeks five and six. After the intervention phase has ended, control participants will complete two additional study assessment visits (visits three and four) to obtain post-intervention measurements. These visits will be a repeat of assessment visits one and two (excluding the pre-exercise screening in visit two).

Participants randomised to the exercise training group will complete 24 exercise training sessions (35 to 50 min of moderate-intensity exercise) during the six-week intervention. Four training sessions will be completed each week, with at least one of these sessions being supervised by the study team. Participants will have the option to undergo these sessions at Loughborough University (National Centre of Sport and Exercise Medicine), Nottingham (Queens Medical Centre Hospital) or Leicester (Leicester General Hospital) depending on preference. The remainder of the sessions each week to be completed by participants will be unsupervised sessions of brisk walking which will be recorded via a heart rate monitor and watch. Participants will be supported after each unsupervised session via a telephone call from a member of the research team and the intensity and duration of the session will be recorded from the watch. Participants in the exercise group will wear a wrist-worn movement sensor throughout the entire training phase and will complete weighed food diaries (two week and one weekend day) in the fifth and sixth weeks of training.

Exercise training

The exercise training program in Part B of this study is based upon joint guidelines published by the European Association for the Study of Liver Disease (EASL), European Association for the Study of Diabetes (EASD) and European Association for the Study of Obesity (EASO); which state that individuals with NAFLD should aim to complete 150 to 200 min per week of exercise [20]. Participants will therefore complete four, 50 min exercise training sessions each week. Each training session will be composed of moderate-intensity continuous exercise at a target intensity that will be determined using a combination of age-predicted maximum heart rate (70-75%) and RPE (13-14).

During each week of exercise training, participants will complete four exercise training sessions, of which at least one of these sessions will be a supervised training sessions. The duration of exercise training will progress from week one to week six to support participants' completion of the programme (Table 2).

Supervised exercise training sessions will include a 10-minute warm-up and five min cool down at a self-selected light intensity (RPE 11 – ‘fairly light’). All supervised training sessions will take place on a treadmill (walking or jogging); however, a cycle ergometer will be available for participants to use should they feel discomfort with prolonged upright exercise. Supervised training sessions will occur Monday to Friday.

Participants will undertake the non-supervised training sessions in their habitual environment e.g. local park. In these sessions, participants will undertake brisk walking at an intensity corresponding to 70-75% of maximum age-predicted heart rate and/or an RPE of 13-14. The intensity and duration of sessions will be monitored using a heart rate monitor and accompanying watch.

Table 2: overview of the supervised & unsupervised moderate-intensity continuous exercise training sessions

	Supervised exercise sessions			Unsupervised exercise sessions	
Training Week	Warm up duration (min)	Cool down duration (min)	Main body duration (min)	Brisk walking session duration (min)	Total weekly exercise duration (min)
1	10	5	20	45	150
2	10	5	25	45	165
3	10	5	30	45	180
4	10	5	30	50	185
5	10	5	35	50	200
6	10	5	35	50	200

NB: four exercise training sessions will be completed each week, of which at least one session will be a supervised exercise training session and the remainder will be an unsupervised session.

Given funding limitations, control participants will not be offered the exercise intervention at the end of the study. Instead, the research team will offer to provide support to participants wishing to become more active beginning with a discussion of their physical activity and fitness data obtained from the study.

Remuneration and expenses

Participants will not be paid for their participation in Part A or B of this study. Travel expenses will be provided for participants

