8. OBJECTIVES

Co-primary objectives

To determine: a) whether differences exist in the liver saturated fat index between obese men with NAFLD, with versus without, T2DM; b) the impact of six weeks exercise training on these outcomes in obese men with NAFLD and T2DM/prediabetes.

Secondary objectives

- To characterise potential differences in the following outcomes between obese men with NAFLD and T2DM versus non-diabetic obese men with NAFLD
 - Liver unsaturated fat index
 - Liver polyunsaturated fat index
 - Total liver fat percentage
 - Liver inflammation
 - Visceral adipose tissue
 - Circulating cardiometabolic biomarkers
 - Circulating liver enzymes
 - Circulating hepatokines
 - Objectively measured sedentary time and physical activity
 - Energy and macronutrient intake
 - Body weight & body fat percentage
 - Blood pressure
 - Aerobic fitness (peak oxygen uptake)
- To determine the impact of six weeks moderate-intensity exercise training on the following outcomes in obese men with NAFLD and T2DM/prediabetes
 - Liver unsaturated fat index
 - Liver polyunsaturated fat index
 - Total liver fat percentage
 - Liver inflammation
 - Visceral adipose tissue
 - Circulating cardiometabolic biomarkers
 - Circulating liver enzymes
 - Circulating hepatokines

- Objectively measured sedentary time and habitual physical activity
- Energy and macronutrient intake
- Body weight and body fat percentage
- Blood pressure
- Aerobic fitness (peak oxygen uptake)

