Participants randomised to control will receive no interventions and will be requested to maintain their habitual lifestyle during the six week intervention phase. Ahead of week five, participants will be posted a wrist worn physical activity monitor to wear continuously for the final two weeks of the study.

Participants will also complete a food diary during this time (two week and one weekend day in week five and six).

Participants randomised to the exercise training intervention will complete 24 moderate-intensity exercise training sessions over the subsequent six weeks (four times per week; ~50 min per session). Each week, at least one of the four exercise training sessions will be supervised by the research team. The remainder of the sessions each week will be unsupervised but monitored objectively using a heart rate monitor. Post- intervention assessments will be completed 48 h - 72 h after the final exercise training session.

After the intervention phase, participants will attend two final assessment sessions to obtain post-intervention data. Assessment visit three will be a repeat of assessment visit one whilst assessment visit four will be a repeat of assessment visit two (minus the medical examination).

[figure not shown]

Figure 1: flow diagram of the study protocol
 SPMIC – Sir Peter Mansfield Imaging Centre; QMC – Queens Medical Centre, Nottingham; LDC – Leicester Diabetes Centre; LU – Loughborough University

Primary and secondary endpoints / outcome measures

Co-primary outcomes: Liver saturated lipid index (%) determined by proton magnetic resonance spectroscopy (¹H-MRS) using a 3T MRI scanner

- 1) Comparison between obese men with NAFLD versus obese men with NAFLD and T2DM (Part A)
- 2) Response to the six week exercise training intervention (Part B)

Secondary outcomes:

- Liver unsaturated lipid index (%) - measured using ¹H-MRS
- Liver polyunsaturated lipid index (%) - measured using ¹H-MRS
- Total hepatic lipid composition (%) - measured using ¹H-MRS
- Liver inflammation - measured using MRI
- Visceral adipose tissue - measured using MRI
- Subcutaneous abdominal adipose tissue - measured using MRI
- Body mass and body fat percentage
- Blood pressure
- Aerobic fitness (peak oxygen uptake)
- Circulating metabolic biomarkers (fasted blood sample)
 - Liver enzymes
 - Glucose
 - Insulin
 - Lipids
 - HbA1c
 - HOMA-IR (surrogate marker of peripheral insulin resistance)
 - ADIPO-IR (surrogate marker of adipose tissue insulin resistance)

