 - Inflammatory proteins
 - Hepatokines
- Objectively measured sedentary time & physical activity assessed via the GENEactiv physical activity monitor
- Energy and macronutrient intake (two weekdays and one weekend day)

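### Two Part B secondary outcomes are not secured as written: the control food-diary weeks conflict, and the exercise arm's sensor record mixes prescribed sessions with habitual activity

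*Protocol*

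**What the plan says.** **Activity.** Among the Part B secondary objectives, section 8 lists "Objectively measured sedentary time and habitual physical activity". The outcome list in section 9 words it as "Objectively measured sedentary time & physical activity assessed via the GENEactiv physical activity monitor", without the word *habitual*. At baseline every man is given a monitor "that they will wear 24 h/day for the next seven days" (section 11). During the intervention, section 11 says of controls: "participants will be posted a physical activity monitor to wear continuously during week five and six"; sections 9 and 12 give them the same two weeks. For the other arm, section 12 says: "Participants in the exercise group will wear a wrist-worn movement sensor throughout the entire training phase". For unsupervised sessions, section 12 commits to recording intensity and duration from the watch. Table 1 lists heart rate and RPE for training.

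**Diet.** The section 9 outcome is "Energy and macronutrient intake (two weekdays and one weekend day", closed there by a bracket. For controls, section 11 says: "Participants will also complete weighed food diaries during week five (two weekdays and one weekend day". Section 9 instead has them record "two week and one weekend day in week five and six", and section 12 also places their food recording in weeks five and six. Section 12 places the exercise arm's diaries in the fifth and sixth weeks.

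**Analysis.** Section 14 says that secondary outcomes follow methods similar to the main analysis.

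**The concern.** Diet and activity outside training are two of the main things a reader will check before crediting the training itself with a change in liver fat composition. The trial is an unblinded lifestyle comparison with 13 men per arm.

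If controls keep the diary in one week and the exercise arm keeps it across two, intake is sampled differently by arm. Diary days never collected cannot be recovered at analysis.

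For activity, the unsupervised sessions are brisk walks in the man's usual surroundings. A wrist sensor has no means of telling them from habitual walking. If the whole record is reported as habitual activity, the comparison partly restates the prescription. It would not show whether men in the exercise arm moved less, or sat more, during the rest of the day.

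**Working it through.** **1. Diary weeks, side by side**

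| Place | Arm | Diary weeks |
|---|---|---|
| Section 9, Summary of trial design | Control | 5 and 6 |
| Section 11, Six week intervention | Control | 5 only |
| Section 12, Overview of procedures | Control | 5 and 6 |
| Section 12, Overview of procedures | Exercise | 5 and 6 |

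One of the three control statements disagrees with the other two and with the exercise arm.

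**2. Diary days.** Two weekdays and one weekend day spread over two weeks can mean three days in all, or three in each week (six).
- Both arms on the weeks 5-6 wording, read the same way: 3 v 3 or 6 v 6 days. The ratio of the within-person error SDs of mean intake is 1.
- Controls on section 11 (3 days), exercise arm on the three-day reading: ratio 1, but the weeks can differ.
- Controls on section 11 (3 days), exercise arm on the six-day reading: ratio √(6/3) = 1.41, with the larger error in controls.

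The last line is the worst pairing. It assumes independent days with equal variance.

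**3. Session time in Table 2 (section 12).** Let s be the number of supervised sessions out of four each week. Then

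weekly total = s × (10 + 5 + main body) + (4 − s) × brisk walk.

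With s = 3 this gives 150, 165, 180, 185, 200 and 200 min for weeks 1-6, which is exactly the printed column. With s = 1, the minimum in the current text, it gives 170, 175, 180, 195, 200 and 200. In weeks 5 and 6 the total is s × 50 + (4 − s) × 50 = 200 min for every s, so that figure does not depend on the supervision pattern. Over the two weeks it comes to 400 min, and 200/7 = 28.6 min/day.

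**4. Moderate-intensity part in weeks 5-6.** The 10-minute warm-up and 5-minute cool-down of a supervised session are at light intensity. Unsupervised walks are taken as wholly at target intensity. Moderate time is then 200 − 15s:

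| s | min/week | min/day |
|---|---|---|
| 1 | 185 | 26.4 |
| 2 | 170 | 24.3 |
| 3 | 155 | 22.1 |
| 4 | 140 | 20.0 |

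**5. Effect of the window.** Weeks 1-6 contain weeks 5-6, so a common 14-day window exists. If the exercise arm were averaged over all six weeks instead, mean session time would be 1,080/6 = 180 min/week on the printed totals, or 1,120/6 = 186.7 with s = 1, against 200 in weeks 5-6. The choice of window alone moves the figure by 13 to 20 min/week. Aligning the windows does not remove the sessions: the 400 min remain inside weeks 5-6.

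**The case against.** The strongest reply is that the activity data are adequate and only their processing is open. The exercise arm's wear period covers the control period in full, no section prescribes averaging over six weeks, and the comparison window and treatment of session time are commonly fixed in a statistical analysis plan, which is not shown here. That stands. The absence of such a rule from the protocol is not in itself a fault.

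It can also be said that *habitual* appears only in the section 8 objective and in section 12's account of control recording, and that including the sessions is right if total activity is meant. That stands too, but it shows that the protocol uses two descriptions of one outcome, and they ask different questions.

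On diet, two of the three control statements already match the exercise arm, and if three days is the total, the day counts agree even under section 11. This limits the size of the problem but does not remove the conflict over weeks.

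A reader might go further and infer that neither outcome compares like with like, that activity outside sessions cannot be studied, or that the recorded activity is largely the intervention itself. The documents do not support these readings. A matched window is available, the diary wording matches on most readings, and no baseline activity level is given from which the sessions' share could be worked out. Nor should 28.6 min/day be read as moderate activity, because it includes light warm-up and cool-down.

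**Conclusion.** The point holds for two secondary outcomes.

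The diary schedule is a plain contradiction about data collection. Its consequence ranges from a mismatch of one week with equal day counts to, at worst, half as many diary days in controls.

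The activity outcome is described in two ways. As collected, the exercise arm's record holds 200 min/week of prescribed sessions in weeks 5-6, of which 140-185 min/week is moderate. To take it as habitual activity would count that as an effect on behaviour. Separating the sessions later needs their clock times, and the protocol commits only to intensity and duration. The watch may store times, but no section says that they will be kept.

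These conclusions assume that the exercise arm's movement sensor is comparable with the control arm's monitor and that sessions are done as Table 2 lays out. The co-primary outcome is not touched.

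**What to change.** 1. Reconcile sections 9, 11 and 12 so that both arms keep the same number of weighed diary days in the same week(s), and state whether the total is three or six days. Where diaries have already been kept, record which days and weeks each man completed.
2. Use one description of the Part B activity outcome in sections 8 and 9. Compare weeks 5-6 in both arms, and report total activity and activity outside training sessions as separate quantities.
3. Record the start time of every supervised and unsupervised session alongside intensity and duration, so that session time can be removed from the sensor record.

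The cost is a wording change, one extra item in the session record and a short processing step. The exercise arm's sensor data from weeks 1-4 leave the between-arm comparison, though they can still describe adherence.
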